5.1.10 Review previous and concomitant medications

5.1.11 Blood collection for general health assessment

CBC with differential, CMP, Phosphorus, Magnesium. Phosphorus and Magnesium will be assessed at C1D1 only.

5.1.12 Blood draw for tumor assessment

CA-19-9, C-reactive protein (CRP). CRP will be assessed at C1D1 only.

5.1.13 Blood draw for fat soluble vitamin levels

Serum levels of Vitamins A (serum retinol), D (25-Hydroxy), E (serum alphatocopherol), and K (PIVKA-II and prothrombin time).

5.1.14 Research blood draw

See Section 7.0 for details. 8 hour fast is required. Morning blood draw is required.

5.1.15 Stool sample

A stool collection kit will be given to the patient during physical exam, where patient will be advised to follow instructions on kit and bring their sample into laboratory as

instructed (see Sections 5.2 and 5.3.2). Microbiome analysis and fecal elastase will be measured from collection of stool sample (Section 8). Fecal elastase will be measured at baseline only.

5.1.16 Hand grip and 15 ft walk test

Hand grip using the hand-held dynanometer. Three assessments for each hand will be completed and recorded. A timed walk-test from first foot fall to last foot fall over 15 feet will be performed twice per assessment.

5.1.17 Bionutrition assessment

ASA-24 (24-hour food recall) and taste and smell alteration. ASA-24 is completed electronically and may be completed within 7 days of the study visit.

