2.2 Secondary Objectives

- 2.2.1 Measure weight stability at baseline and day 1 of every cycle for 6 months
- **2.2.2** Record 24-hour caloric intake at C1D1, C3D1, and end-of-study
- 2.2.3 Assess stool frequency at C1D1 and C3D1
- 2.2.4 Stool consistency at C1D1 and C3D1
- 2.2.5 Measurement of fat-soluble vitamins at baseline and end-of-study
- **2.2.6** Evaluate microbiome at C1D1 and C3D1
- 2.2.7 Determine if pancreatic enzyme replacement therapy is associated with increased daily activity (steps, counts, stairs, sleep, heart rate, active minutes) using a wristworn fitness tracker (e.g., Fitbit)

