5.2 Screening/Baseline Procedures

Assessments performed exclusively to determine eligibility for this study will be done only after obtaining informed consent. Assessments performed for clinical indications (not exclusively to determine study eligibility) may be used for baseline values even if the studies were done before informed consent was obtained.

All screening procedures used for eligibility verification must be performed within 4 weeks of Day 1 unless otherwise stated. Baseline procedures not required for eligibility verification can occur on Cycle 1, Day 1 of treatment (See section 5.3).

The screening and baseline procedures include:

- Informed consent
- Eligibility review, including:
 - Pregnancy test
- Demographics
- Medical/Surgical history
- Complete physical exam
- Standard of care CT imaging
- Height, weight, vital signs
- Performance status (ECOG or Karnofsky)
- AE (baseline symptom) assessment

- Concomitant medications review
- Labs: CBC/diff, CMP
- Blood draw for fat soluble vitamin levels
- Fecal elastase
 - Note: for maximum flexibility for the patients, the fecal elastase stool sample may be collected during screening or until C1D1 (+ 7 days).
 Patients will be encouraged to provide the fecal elastase stool sample prior to starting treatment, if possible.

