5.3 Procedures During Treatment

These visits can occur within a window of -/+ 7 business days of the anticipated visit date to account for clinic closures or holidays and to align with the standard of care chemotherapy administration schedule.

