5.3.2 Day 1 of Every Other Cycle (every 8 weeks)

- Research blood (See Section 7). 8 hour fast is required. Morning blood draw is required.
- Self-administered QOL surveys: PROMIS-29, FAACT (APPENDICES C, D)
- Frailty status (hand grip; 15 ft walk-test Appendix E)
- Bionutrition assessment (ASA-24 +taste and smell alteration) conducted by study staff (Appendix B) (C1D1, C3D1 only)
- Stool sample for microbiome analysis (Section 8) (C1D1 and C3D1 only)
 - Note: for maximum flexibility for the patients, the C1D1 microbiome stool sample may be collected during screening or until C1D1 (+ 7 days). Patients will be encouraged to provide the microbiome stool sample prior to starting treatment if possible. If collected during screening, the microbiome sample will be stored until eligibility is confirmed; if the patient results in a screen fail, the sample will be destroyed unless consent is granted for its use on another IRB-approved protocol, e.g., GI-Bank protocol (IRB# Pro00054363).
 - Note: for maximum flexibility for the patients, the C3D1 microbiome stool sample may be collected +/- 7 days of C3D1.
- Stool survey (C1D1 and C3D1 only)

5.3.3 End-of-Treatment Visit (EOT), +7 days.

Subjects will continue to take the study drug until the Cycle 6 Day 28 time point. Subjects should be reminded to discontinue study supply of Pancreaze following Cycle 6 Day 28. Up to seven days following the last dose, there will be an EOT visit for subjects to return pill bottles and to transition to SoC enzymes, if applicable.

- Safety evaluation (As per CTCAE grading)
- Return pill bottles
- Transition to SoC enzymes (if applicable)

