5.7 Removal of Subjects from Study

Patients can be taken off the study treatment and/or study at any time at their own request, or they may be withdrawn at the discretion of the investigator for safety, behavioral or administrative reasons. The reason(s) for discontinuation will be documented and may include:

³ASA-24 is completed electronically and may be completed within 7 days of the visit.

⁴Subjects will complete a daily compliance diary for the first two cycles only. Diary will be given to patients on Day 1 of the first two cycles. Subjects will return diary to study staff for compliance calculation on completion of each of the first two cycles.

⁵Fat-soluble vitamin labs to be drawn include: Vitamin A: serum retinol; Vitamin D:25-Hydroxy; Vitamin E: serum alpha-tocopherol; Vitamin K: PIVKA-II and prothrombin time.

⁶The patients will be followed on treatment for the 24-week study treatment period. Treatment may continue beyond the study treatment period, at the physician's discretion, per standard of care. Pancreaze will be dispensed at C1D1 and C4D1, and subjects will return remaining supply at C4D1 and the end-of-treatment visit for drug accountability by Research Pharmacy.

⁷Stool sample may be collected during screening or until C1D1 + 7 days.

⁸ Window for C3D1 sample is +/- 7 days.

⁹Subjects will continue to take the study drug until the Cycle 6 Day 28 time point. Subjects should be reminded to discontinue study supply of Pancreaze following Cycle 6 Day 28.

- **5.7.1** Patient voluntarily withdraws (follow-up permitted);
- **5.7.2** Patient withdraws consent (termination of treatment and follow-up);
- **5.7.3** Patient is unable to comply with protocol requirements;
- **5.7.4** Patient experiences toxicity that makes continuation in the protocol unsafe;
- **5.7.5** Treating physician judges continuation on the study would not be in the patient's best interest;
- **5.7.6** Patient becomes pregnant (pregnancy to be reported along same timelines as a serious adverse event);
- 5.7.7 Lost to follow-up. If a research subject cannot be located to document survival after a period of 2 years, the subject may be considered "lost to follow-up." All reasonable efforts must be made to locate subjects to determine and report their ongoing status. Lost to follow-up is defined by the inability to reach the subject after a minimum of three documented phone calls, faxes, or emails as well as lack of response by subject to one registered mail letter.

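### The C1D1 food recall, the only baseline for caloric intake, may be completed after Pancreaze has started, because its 7-day window has no direction and no pre-dose rule

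*Combined protocol and SAP*

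**What the plan says.** Caloric intake is a secondary objective in Section 2.2: "Record 24-hour caloric intake at C1D1, C3D1, and end-of-study". The Study Summary lists the same objective and calls the first of the three time points baseline. Section 5.3.2 and the Time and Events Table place the ASA-24 at C1D1 and C3D1 during treatment, Section 5.4 adds the End-of-Study visit, and the screening list in Section 5.2 does not include it.

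On timing, Section 5.1.17 says "ASA-24 is completed electronically and may be completed within 7 days of the study visit", and footnote 3 of the Time and Events Table repeats this in almost the same words. Neither place says whether the 7 days run before the visit, after it, or both.

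On the start of treatment, footnote 6 of the same table says "Pancreaze will be dispensed at C1D1 and C4D1", and the table shows Pancreaze taken daily. Section 5.2 adds that "Baseline procedures not required for eligibility verification can occur on Cycle 1, Day 1 of treatment", without ordering those procedures relative to the first dose.

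For the C1D1 microbiome stool sample, which may be collected up to 7 days after C1D1, Section 5.3.2 says "Patients will be encouraged to provide the microbiome stool sample prior to starting treatment if possible". Section 5.2 has a similar sentence for fecal elastase. There is no such sentence for the ASA-24.

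**The concern.** A baseline should describe the patient before the intervention. Here a patient can receive capsules at C1D1, take them for several days, complete the recall within the permitted window, and have that on-enzyme day filed as baseline with no deviation from the protocol.

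Section 2.4.2 hypothesises that enzyme supplementation will increase caloric intake. The trial has one arm, so the evidence has to come from comparing recalls within the treated patients. The End-of-Study recall cannot stand in for a lost baseline or for C3D1: it takes place about 30 days after the last study dose, once the study supply has been returned and patients have moved to standard-of-care enzymes where applicable (Sections 5.3.3 and 5.4). C1D1 against C3D1 is therefore the only comparison of intake before the study drug with intake on it. If some C1D1 recalls are already on drug, no other scheduled recall can replace them, and Section 9.2 has no rule for recognising them.

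**Working it through.** The plan gives no sample size, effect size, standard deviation or power for caloric intake, so there is no figure to reproduce. Two checks are possible.

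**1. Which completion days the window permits**

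Inputs: a 7-day window with no sign (Section 5.1.17, footnote 3); dispensing at C1D1 (footnote 6). Assumption: the first dose is taken on the day of the C1D1 visit, counted here as day 0.

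| Reading of the window | Permitted days | Days after C1D1 | Share |
|---|---|---|---|
| Either side (-7 to +7) | 15 | 7 | 7/15 = 47% |
| After only (0 to +7) | 8 | 7 | 7/8 = 88% |
| Before only (-7 to 0) | 8 | 0 | 0% |

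A recall done on day +1 looks back over 24 hours that may be only partly on enzymes. From day +2 onward the recalled period lies wholly after the first dose: 6 of 15 days, or 6 of 8. These are counts of what is allowed. They do not predict when patients will complete the form.

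The visit window does not create or cure the problem. Section 5.3 says "These visits can occur within a window of -/+ 7 business days of the anticipated visit date", but dispensing is tied to the C1D1 visit, so visit and first supply move together. The recall window is what separates the baseline from the start of treatment.

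**2. What a post-dose baseline does to the contrast**

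Let D be the true difference in mean intake between before treatment and C3D1, f the share of baseline recalls completed after the first dose, and g the share of D already present at those recalls.

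- Mean at C1D1 = pre-treatment mean + f x g x D
- Mean at C3D1 = pre-treatment mean + D
- Observed contrast = D x (1 - f x g), a reduction of f x g

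Neither f nor g can be taken from the documents. As illustrations under assumed inputs only:

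- g = 0 (no effect on intake in week 1): reduction 0, whatever f is
- f = 0.25, g = 0.25: 0.25 x 0.25 = 0.0625, about 6%
- f = 0.5, g = 0.5: 0.25, or 25%
- f = 1, g = 0.5: 0.5, or 50%

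The formula applies to a difference of means. Section 9.2 does not name a change-from-baseline test. It describes summaries, regression on baseline variables and random effects for repeated measures. C1D1 is still the first time point in any of these, so a post-dose recall enters as if it were pre-treatment.

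**The case against.** The other side has several fair points.

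- **Intent is clear.** The Study Summary calls the first recall baseline, and on the either-side reading a patient may already complete it before C1D1. That is so, but permitting a pre-dose recall does not require one, and the after-only reading leaves at most the visit day itself.
- **The window is unsigned, not two-sided.** The protocol writes a sign elsewhere when it wants one, so either side is a reading and not the text. This stands. The point does not depend on it, because the after-only reading has the same fault to a larger degree.
- **The size is unknown.** The background sections report weight and fat absorption over weeks, not how soon intake changes. This stands, and the illustrations above must not be quoted as estimates of bias.
- **Flexibility is deliberate.** The stool samples have similar latitude for patients' convenience. But there the protocol also encourages collection before treatment, and an electronic questionnaire is easier to complete early than a stool sample.
- **Discarding post-dose baselines would be costly** with about 30 evaluable patients, 10 per stage. This is reasonable, and it favours flagging with a sensitivity analysis over exclusion.

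A reader might also infer that the window confounds enzyme and chemotherapy effects, because visits may move "to align with the standard of care chemotherapy administration schedule" and the C1D1 and C3D1 recalls could fall on opposite sides of an infusion. The documents do not support this as a finding. They give no regimen, cycle length or infusion day, and do not say that an infusion takes place on Day 1. A distance in days between recalls also says little about position within a repeating schedule of unknown length.

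**Conclusion.** The point holds as a gap in the timing rule for one secondary endpoint. As written, the protocol allows the sole baseline recall for caloric intake to describe a day on Pancreaze, and nothing in the analysis plan identifies such a recall. This follows from the text under either of the two readings that allow completion after the visit. It disappears only under a before-only reading that is not stated.

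The consequence is conditional. If intake rises within the first week on enzymes, the C1D1-to-C3D1 contrast is smaller than the true effect. If it does not, nothing is lost. It rests on the first dose being taken at or soon after C1D1 and on some patients using the later part of the window, and the documents give no figure for how many would. A recall completed on or before C1D1, ahead of the first dose, remains a valid baseline. It would be too strong to say that the caloric-intake result will be biased, or by a given percentage. The primary compliance endpoint is untouched. The amendment is worthwhile mainly because it is so cheap.

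**What to change.** In Sections 5.1.17 and 5.3.2 and in footnote 3 of the Time and Events Table:

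- Require the C1D1 ASA-24 to be completed in the 7 days up to and including Day 1, before the first Pancreaze dose. The link can be sent once consent is signed.
- Use the same direction at C3D1 for consistency: in the 7 days up to and including the visit.
- Record the completion date of each recall and compare the C1D1 date with the first entry in the daily accountability log.

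In Section 9.2, flag any C1D1 recall completed after the first dose as post-dose, and repeat the caloric-intake analysis without the flagged recalls. For patients already enrolled, the flag can be applied wherever completion dates are available.

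This sets the timing of a questionnaire and leaves treatment as it is. The cost is a wording amendment, one date field and one sensitivity analysis. The downside is a few missing or late baseline recalls. While these sections are open, reconcile who completes the ASA-24: Section 5.3.2 has study staff conducting it, while Section 2.5.2 names a self-administered tool.

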5.1.18 Patient reported outcomes

Patient reported outcomes (Quality-of-life questionnaire: PROMIS-29; FAACT)

5.1.19 Self-reported daily Pancreaze accountability log and compliance calculation

Subjects will record usage of Pancreaze in a daily log. Subjects will return log to study staff at study visits for compliance calculation.

5.1.20 Activity Monitoring

Wearable activity monitor (e.g., Fitbit Charge HR) activity monitoring to measure step count, heart rate, activity intensity, stairs climbed and sleep. Provide wearable activity monitor with charger and instructions for activity monitoring. Wearable activity monitor will be paired to the subject's personal smartphone. Subject may keep or return the wearable activity monitor at the end-of-study visit. Continued collection of activity monitor data during follow-up will be optional.

5.1.21 Survival follow-up

Per Section 5.5.

5.2 Screening/Baseline Procedures

Assessments performed exclusively to determine eligibility for this study will be done only after obtaining informed consent. Assessments performed for clinical indications (not exclusively to determine study eligibility) may be used for baseline values even if the studies were done before informed consent was obtained.

All screening procedures used for eligibility verification must be performed within 4 weeks of Day 1 unless otherwise stated. Baseline procedures not required for eligibility verification can occur on Cycle 1, Day 1 of treatment (See section 5.3).

The screening and baseline procedures include:

- Informed consent
- Eligibility review, including:
 - Pregnancy test
- Demographics
- Medical/Surgical history
- Complete physical exam
- Standard of care CT imaging
- Height, weight, vital signs
- Performance status (ECOG or Karnofsky)
- AE (baseline symptom) assessment

- Concomitant medications review
- Labs: CBC/diff, CMP
- Blood draw for fat soluble vitamin levels
- Fecal elastase
 - Note: for maximum flexibility for the patients, the fecal elastase stool sample may be collected during screening or until C1D1 (+ 7 days).
 Patients will be encouraged to provide the fecal elastase stool sample prior to starting treatment, if possible.

5.3 Procedures During Treatment

These visits can occur within a window of -/+ 7 business days of the anticipated visit date to account for clinic closures or holidays and to align with the standard of care chemotherapy administration schedule.

5.3.1 Day 1 of Every Cycle (each 4 weeks/28 days)

- Treatment as per dosing schedule
- Completion of study dosing diary for the first two cycles only
- Safety evaluation (As per CTCAE grading)
- Physical Exam
- Weight
- Vital signs
- ECOG or Karnofsky performance status (Appendix A)
- Concomitant medications
- Blood collection (CBC with differential, CMP)
- CMP add-ons (Phos, Mag) (C1D1 only)
- Tumor markers (CA 19-9)
- CRP (C1D1 only)
- Assess wearable activity monitor functionality

5.3.2 Day 1 of Every Other Cycle (every 8 weeks)

- Research blood (See Section 7). 8 hour fast is required. Morning blood draw is required.
- Self-administered QOL surveys: PROMIS-29, FAACT (APPENDICES C, D)
- Frailty status (hand grip; 15 ft walk-test Appendix E)
- Bionutrition assessment (ASA-24 +taste and smell alteration) conducted by study staff (Appendix B) (C1D1, C3D1 only)
- Stool sample for microbiome analysis (Section 8) (C1D1 and C3D1 only)
 - Note: for maximum flexibility for the patients, the C1D1 microbiome stool sample may be collected during screening or until C1D1 (+ 7 days). Patients will be encouraged to provide the microbiome stool sample prior to starting treatment if possible. If collected during screening, the microbiome sample will be stored until eligibility is confirmed; if the patient results in a screen fail, the sample will be destroyed unless consent is granted for its use on another IRB-approved protocol, e.g., GI-Bank protocol (IRB# Pro00054363).
 - Note: for maximum flexibility for the patients, the C3D1 microbiome stool sample may be collected +/- 7 days of C3D1.
- Stool survey (C1D1 and C3D1 only)

5.3.3 End-of-Treatment Visit (EOT), +7 days.

Subjects will continue to take the study drug until the Cycle 6 Day 28 time point. Subjects should be reminded to discontinue study supply of Pancreaze following Cycle 6 Day 28. Up to seven days following the last dose, there will be an EOT visit for subjects to return pill bottles and to transition to SoC enzymes, if applicable.

- Safety evaluation (As per CTCAE grading)
- Return pill bottles
- Transition to SoC enzymes (if applicable)

5.3.4 Standard of care CT imaging

As indicated per standard of care, approximately every 8 weeks

5.4 End-of-Study Visit

- The End-of-Study visit is to occur 30 days following last dose of study treatment, +/- 7 days.
- Research blood (See Section 7). 8 hour fast is required. Morning blood draw is required.
- Safety evaluation (As per CTCAE grading)
- Physical Exam
- Weight
- Vital signs
- ECOG or Karnofsky performance status (Appendix A)
- Concomitant medications
- Blood collection (CBC with differential, CMP)
- Tumor markers (CA 19-9)
- Fat soluble vitamin levels
- Frailty status (hand grip; 15 ft walk-test Appendix E)
- Bionutrition assessment (ASA-24 +taste and smell alteration) conducted by study staff (Appendix B)
- Self-administered QOL surveys: PROMIS-29, FAACT (APPENDICES C, D)
- Assess wearable activity monitor functionality

5.5 Follow-up Procedures

Patients will be followed every 6 months for 36 months after completion of (or early withdrawal from) study treatment or until death.

If there is no record of patient survival in medical chart by review, a phone call will be made to assess survival. Physical exam, weight, vital signs, and ECOG or Karnofsky performance status will also be collected from the medical record if available per standard of care.

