2.5.2 Secondary endpoints

- Measure weight stability at baseline and day 1 of every cycle for 6 months
- Food intake will be assessed by study staff at C1D1, C3D1, and end-ofstudy. A validated 24-hour recall questionnaire will be analyzed using the automated self-administered 24-hour Dietary Assessment tool (ASA-24)
- Assess stool frequency at C1D1 and C3D1 using a stool survey
- Stool consistency at C1D1 and C3D1
- Measurement fat-soluble vitamins (including Vitamins A, D, E, and K) at baseline and end-of-study
- Evaluate microbiome at C1D1 and C3D1
- Activity (steps taken, stairs climbed, sleep duration and disturbances, heart rate and intensity) will be collected using the wearable activity monitor (e.g., Fitbit Charge HR) daily for the duration of the study.

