4.3 Duration of Follow-up

Patients will undergo an End of Study assessment 30 days after completion of the 24-week study treatment period. Patients removed from treatment for unacceptable adverse events will then be followed until resolution or stabilization of the adverse event and will continue to be followed for the duration of the study as per protocol. After the End of Study Assessment, follow-up will involve every 6-month phone calls to collect survival data for 36 months.

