5.6 Time and Events Table

	Screening / Baseline	Treatment		Follow	v-up Phase
Procedures		Every Cycle (Every 4 weeks)	End of Treatment ⁹	End-of- Study Visit	Survival
Frocedures	Within 4 weeks of Day 1	Cycles 1, 2, 3, 4, 5, 6 (Weeks 0, 4, 8, 12, 16, 20)	End of Week 24 (+ 7 days)	30 days after treatment	Follow-up Every 6 months for 36 months (+/7 days)
		Day 1 (+/- 7 days)		termination (+/- 7 days)	(// 22,5)
Informed Consent	x				
Eligibility review	Х				
Pregnancy test	Х				
Demographics	Х				
Medical / Surgical History	X				
Complete Physical Exam	Х	Х		Х	Х
Standard of Care CT imaging		As per standard of care, approximately every 8 weeks			
Height	X				
Weight	Х	X		Х	Х
Vital Signs	Х	X		X	X
Performance Status (ECOG or Karnofsky)	x	X		X	X
Adverse Event Assessment	Х	х	Х	х	
Concomitant Medications	Х	х		х	
Blood collection (CBC, CMP)	Х	х		Х	
CMP add-ons (Phos, Mag)		X (C1D1 only)			

	Screening / Baseline	Treatment		Follow	/-up Phase
Dragodiuse		Every Cycle (Every 4 weeks)	End of Treatment ⁹	End-of- Study Visit	0
Procedures	Within 4 weeks of Day 1	Cycles 1, 2, 3, 4, 5, 6 (Weeks 0, 4, 8, 12, 16, 20)	End of Week 24 (+ 7 days)	30 days after treatment	Survival Follow-up Every 6 months for 36 months (+/7 days)
		Day 1 (+/- 7 days)		termination (+/- 7 days)	, ,
CA 19-9 (biomarker)		X		х	
C-reactive protein (CRP)		X (C1D1 only)			
Fat soluble vitamin levels ⁵	Х			Х	
Research Blood Tests		X ¹		Х	
Stool Sample Microbiome and Stool Survey		X (C1D1 ⁷ and C3D1 ⁸ only)			
Fecal elastase	X ⁷				
Hand grip and 15 ft walk test		X ¹		Х	
Bionutrition assessment: ASA-24 (24-hour food recall) ³ ; taste and smell alteration		X (C1D1 and C3D1 only)		Х	
Self-administered QOL survey: PROMIS-29; FAACT		X ¹		Х	
Pancreaze treatment		X (daily) ⁶			
Self-reported daily Pancreaze accountability log and compliance calculation ⁴		х			
Physical Activity: Assess wearable activity monitor functionality		Х		Х	
Wearable activity monitoring			Continuous	S	X ²
Return research pill bottles/transition to SOC enzymes			Х		

	Screening / Baseline	Treatment		Follow	/-up Phase
Dresselves		Every Cycle (Every 4 weeks)	End of Treatment ⁹	End-of- Study Visit	0 000
Procedures	Within 4 weeks of Day 1	Cycles 1, 2, 3, 4, 5, 6 (Weeks 0, 4, 8, 12, 16, 20)	End of Week 24 (+ 7 days)	30 days after treatment	Survival Follow-up Every 6 months for 36 months (+/7 days)
		Day 1 (+/- 7 days)		termination (+/- 7 days)	(177 days)
Survival Follow-up					×

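### After early stopping for a reason other than an adverse event, only one further weight is scheduled inside the 6-month window, so the weight result is likely to lean towards patients who stay on Pancreaze

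*Combined protocol and SAP*

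**What the plan says.** All references are to the combined protocol and SAP.

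- **Endpoint.** Section 2.5.2 lists, first among the secondary endpoints, "Measure weight stability at baseline and day 1 of every cycle for 6 months". It ties the measurement to cycles and gives no numerical definition of stability.
- **Schedule.** In Section 5.6 the four-weekly weights belong to the treatment phase: "Cycles 1, 2, 3, 4, 5, 6 (Weeks 0, 4, 8, 12, 16, 20". The End-of-Treatment column has no weight.
- **After the last dose.** Section 5.4 includes a weight at the closing visit: "The End-of-Study visit is to occur 30 days following last dose of study treatment, +/- 7 days". It makes no distinction by reason for stopping.
- **A different anchor for the same visit.** Section 4.3 says "Patients will undergo an End of Study assessment 30 days after completion of the 24-week study treatment period".
- **Adverse-event removals.** Section 4.3 adds that these patients "will continue to be followed for the duration of the study as per protocol". No section says this for any other reason.
- **Early withdrawal.** Section 5.5 says "Patients will be followed every 6 months for 36 months after completion of (or early withdrawal from) study treatment or until death". Weight and some other items "will also be collected from the medical record if available per standard of care".
- **Voluntary withdrawal.** Section 5.7 lists "Patient voluntarily withdraws (follow-up permitted" but names no visits. Withdrawal of consent ends follow-up.
- **Replacement.** Under Section 4.5 patients who withdraw from study treatment are replaced. The Study Summary allows up to 40 patients for 30 evaluable, and evaluable is not defined for weight.
- **Analysis.** Section 9.2 plans descriptive summaries, then regression with random effects for repeated measures. It does not say how missing weights, discontinuation or death are handled, and it has no sensitivity analysis.

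**The concern.** The reasons for stopping in Section 4.1.4 include intercurrent illness and a change in condition that makes the patient unsuitable for further treatment. In patients enrolled because of cachexia, these are plausibly accompanied by further weight loss. If weights thin out just when such patients stop, the later visits increasingly describe those well enough to continue.

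There is no control arm in which the same selection would show. Replacement adds to the problem if the replaced patients' weights are set aside, and the plan does not say whether they are. At stake is the lead secondary hypothesis in Section 2.4.2, that weight loss is stabilised.

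**Working it through.** The plan has no computed figure for weight, no expected stopping rate and no weight SD, so there is nothing of its own to reproduce. The design figure in Section 9.1 concerns completion at 8 weeks and does not bear on this point.

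**1. Which weights an early stopper has.** Take Section 5.4 at face value. With the last dose at week *s*, the closing visit falls at *s* + 30/7 = *s* + 4.3 weeks, give or take one week.

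| Last dose | Day 1 dates still to come | 30-day weight at about | Day 1 dates after that weight |
|---|---|---|---|
| Week 6 | 8, 12, 16, 20 | week 10.3 | 12, 16, 20 |
| Week 8 | 12, 16, 20 | week 12.3 | 16, 20 |
| Week 12 | 16, 20 | week 16.3 | 20 |
| Week 16 | 20 | week 20.3 | none |

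The break point is *s* + 4.3 = 20, so *s* = 15.7, or about week 16. The first 6-monthly contact comes about 26 weeks after stopping, which is always beyond week 24. For the week 6 stopper it falls at about week 32.

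On the Section 4.3 wording, the closing visit is at 24 + 4.3 = 28.3 weeks. An early stopper would then have no scheduled weight between stopping and week 24.

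**2. Bias of a mean taken in continuers only.** Bias = *f* × *d*, where *f* is the fraction stopping and *d* is the continuers' mean change minus the stoppers'. Both are assumptions:

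- *f* = 0.25 comes from 10/40, the room left for replacement. It is a ceiling on enrolment, not a stopping rate.
- *d* = 1.2 − (−3.7) = 4.9 points borrows the enzyme and placebo arms of the trial cited in Section 1.3. Those arms are not stoppers and continuers. The follow-up was also short: 8 weeks in Section 1.3, and 4 weeks in Section 1.1 beside the same weight figures.

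At *f* = 0.25 the bias is 0.25 × 4.9 = 1.2 points. The mean in everyone is 0.75 × 1.2 − 0.25 × 3.7 = −0.03%, and the continuers show +1.2%. At *f* = 0.10, 0.40 and 0.50 the bias is 0.49, 1.96 and 2.45 points. If *d* = 0, there is no bias.

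If weights are recovered for half the stoppers, and those are typical stoppers, the mean at *f* = 0.25 becomes (0.75 × 1.2 − 0.125 × 3.7)/0.875 = 0.50%. The bias falls to 0.50 + 0.03 = 0.53 points.

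**3. The planned random-effects model.** I simulated 40 patients, 150 runs per setting, with six four-weekly weights after baseline. The assumed mean slope was zero, the slope SD 1 point per cycle and the residual SD 1.2 points. Stopping was 46% to 56%. Entries are mean percent change at the last visit; pairs are the runs without and with one weight after stopping.

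| Stopping driven by | All patients, complete data | Completers only | Model, no later weight | Model, one later weight |
|---|---|---|---|---|
| Nothing related to weight | −0.05 / 0.00 | −0.07 / −0.01 | −0.06 | −0.01 |
| Weights already recorded | −0.06 / −0.01 | 3.53 / 3.57 | −0.03 | 0.02 |
| Underlying, unrecorded trajectory | 0.00 / −0.11 | 3.66 / 3.67 | 1.83 | 0.83 |

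In the last row the model's bias is 1.83 − 0.00 = 1.83 points without a later weight and 0.83 + 0.11 = 0.94 with one. The fitted model has the form that generated the data, which favours it. About half the patients stop, which is not a rate the plan gives. The ordering is informative; the sizes are not forecasts.

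**The case against.** - **Weights do not end at stopping.** A reader might infer that scheduled weights cease with the last dose. Section 5.4 and the table in Section 5.6 provide a weight about 30 days later whatever the reason, and Section 5.5 adds chart weights where available. Patients stopping from about week 16 lose nothing up to week 20. This stands, and it limits the gap to earlier stoppers.
- **No sentence ends the four-weekly visits.** Section 2.5.2 sets no on-treatment condition, and Section 5.7 separates leaving treatment from leaving the study. This also stands: that the visits stop is read from the table layout and Section 5.5. But if continuation was intended for everyone, stating it only for adverse-event removals invites the other reading.
- **The planned model may cope.** It was essentially unbiased in two of the three settings above, and in the third the scheduled 30-day weight roughly halved the bias. This stands for the regression. It does not cover the descriptive means in Section 9.2, which at each visit describe only patients who were weighed.
- **An on-treatment target is arguable.** Section 2.4.2 asks about weight with supplementation, and weights after stopping may reflect other care. That is a reason to report both results, not to leave the choice open.
- **Weight is not the primary endpoint.** The primary endpoint is 8-week compliance (Section 2.5.1), which this point does not touch.

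**Conclusion.** The concern holds as a gap in data collection and analysis. For stopping reasons other than an adverse event, one further weight is scheduled inside the 6-month window, and later Day 1 weights up to week 20 can be absent for patients who stop before about week 16. Sections 4.3 and 5.4 disagree on when the closing visit takes place, and on the Section 4.3 wording even that one weight falls outside the window. With replacement of withdrawals and no rule for discontinuation or death, the 6-month result is likely to lean towards patients who stay on.

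A reader might go further and conclude that the trial will overstate stability by a known amount. The documents do not support that. They give no stopping rate and no difference between stoppers and continuers. The 1.2 points rest on an assumed 25% and an assumed 4.9-point gap, and apply to a continuers-only mean. The random-effects model is biased less, and, if correctly specified, only when stopping depends on weight change not yet recorded. The upward direction rests on the assumption that stoppers lose more weight than continuers, which is plausible in cachexia but not shown.

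**What to change.** - **Sections 5.5 and 5.6.** For every treated patient who stops early for any reason and has not withdrawn consent, abstract from the medical record the clinic weight nearest each remaining scheduled Day 1 through week 20, with its date. This is in addition to the 30-day weight.
- **Sections 4.3 and 5.4.** Reconcile the two timings of the End-of-Study visit, so that it is clear when an early stopper has it.
- **Section 9.2.** Analyse weight in all treated patients, including those who were replaced, with these values in the random-effects model. Report deaths and missing weights by visit. Give the on-treatment-only result as a sensitivity analysis.

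The cost is at most five chart values per early stopper (weeks 4, 8, 12, 16 and 20), with no new visit or procedure. It extends the chart collection that Section 5.5 already allows. It is a partial remedy: patients who no longer attend clinic will still have missing weights, and they may be the ones losing most. That is why missing weights and deaths need to be shown by visit.
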